2 PROTOCOL SUMMARY

2.1 Study objectives

2.1.1 Primary objective

To demonstrate the clinical efficacy of rozanolixizumab in maintenance treatment in study participants with primary ITP.

2.1.2 Secondary objective

To assess the safety and tolerability of rozanolixizumab

2.1.3 Exploratory objectives

- To evaluate the clinical efficacy as measured by the ITP bleeding score
- To assess the effect of rozanolixizumab on health-related quality of life (HRQoL)
- To assess hospitalizations due to ITP
- To assess the effect of rozanolixizumab on patient reported outcomes (PROs)
- To assess the pharmacokinetics of rozanolixizumab administered by subcutaneous (sc) infusion

-
- To evaluate the incidence and emergence of antidrug antibodies (ADAs) of rozanolixizumab
 - To assess the pharmacodynamic (PD) effects of rozanolixizumab
 - To assess the influence of rozanolixizumab treatment on vaccination titers
 - To assess the effect of rozanolixizumab on response to vaccination in study participants who received COVID-19 vaccine

2.2 Study endpoints

2.2.1 Efficacy endpoints

2.2.1.1 Primary efficacy endpoint

Durable Clinically Meaningful Platelet Response of $\geq 50 \times 10^9/L$ for at least 8 out of 12 weeks during the last 12 weeks (Week 13 to 25)

2.2.1.2 Secondary efficacy endpoints

- Cumulative number of weeks with Clinically Meaningful Platelet Response of $\geq 50 \times 10^9/L$ over the 24-week treatment period
- Time to first Clinically Meaningful Platelet Response of $\geq 50 \times 10^9/L$: time from starting treatment to achievement of first response of $\geq 50 \times 10^9/L$
- Clinically Meaningful Platelet Response of $\geq 50 \times 10^9/L$ by Day 8
- Response defined as platelet count $\geq 30 \times 10^9/L$ and at least a 2-fold increase of the Baseline count confirmed on at least 2 separate occasions at two adjacent nominal visits at least 7 days apart, and absence of bleeding by visit^{a,b}
- Time to first rescue therapy
- Change from Baseline to Week 25 in ITP Patient Assessment Questionnaire (ITP-PAQ) Symptoms Score

Notes:

^a Absence of bleeding indicated by Grade 0 for all domains of the skin, mucosae, and organs (SMOG), or a Skin Grade of 0 or 1.

^b Nominal visits are on-site visits where ITP bleeding scale assessment is performed.

2.2.1.3 Other efficacy endpoints

- Duration of first Clinically Meaningful Platelet Response of $\geq 50 \times 10^9/L$: measured from achievement of first Response to loss of Response (loss of Response defined as platelet count $< 50 \times 10^9/L$)
- Time to first Response: time from starting treatment to achievement of Response
- Usage of rescue therapy (Yes/No) by visit
- Complete Response (platelet count): defined as platelet count $\geq 100 \times 10^9/L$ confirmed on at least 2 separate occasions at two adjacent nominal visits at least 7 days apart, and absence of bleeding by visit

-
- Cumulative number of weeks over the planned 24-Week treatment period with platelet counts of $\geq 100 \times 10^9/L$
 - Cumulative number of weeks over the planned 24-Week treatment period with platelet counts $\geq 30 \times 10^9/L$ and at least doubling from Baseline
 - Mean change from Baseline in platelet count by visit
 - Clinically Meaningful Platelet Response of $\geq 50 \times 10^9/L$, for at least 4 out of 6 weeks during the last 6 weeks (Week 19 to 25)
 - Clinically Meaningful Platelet Response of $\geq 50 \times 10^9/L$, for at least 6 out of 8 weeks during the last 8 weeks (Week 17 to 25)

2.2.1.4 Exploratory endpoints

- ITP-specific Bleeding Assessment Tool (ITP-BAT) bleeding events and severity by visit
- Change from Baseline in European Quality of Life-5 Dimension 5 Levels (EQ-5D-5L) item responses
- Change from Baseline in Short form 36-item (SF-36) domain and composite scores
- Change from Baseline in the ITP-PAQ V1 domain Scores
- Number and length of hospitalizations
- Change from Baseline in FATIGUE-PRO Physical Fatigue Score by visit
- Change from Baseline in Patient Global Impression of Severity (PGI-S)
- Patient Global Impression of Change (PGI-C) at all available post-baseline assessments
- Plasma concentration of rozanolixizumab
- ADAs at each scheduled assessment

2.2.1.4.1 Exploratory pharmacodynamic endpoint:

- Total serum IgG (absolute value) and change from Baseline (absolute values and percentage) in serum IgG and in serum IgG subclass concentration at each scheduled assessment
- Absolute values and change from Baseline (absolute values and percentage) in serum immunoglobulin concentrations (IgA, IgE, IgM) at each scheduled assessment

2.2.1.4.2 Other exploratory endpoints

- Percent change from Baseline in vaccination titers against *Streptococcus pneumoniae*, *Neisseria meningitidis*, and *Haemophilus influenzae* in splenectomized study participants
- Percent change from Baseline in vaccination titers against tetanus in all study participants
- Change in biomarkers of COVID-19 vaccine response over time

2.2.2 Safety endpoints

Secondary Safety Endpoints:

-
- Occurrence of treatment-emergent adverse events (TEAEs)
 - Occurrence of TEAEs leading to withdrawal of investigational medicinal product (IMP) (ie, study discontinuation)

2.2.2.1 Other safety endpoints

- Occurrence of serious TEAEs
- Occurrence of treatment related TEAEs
- Occurrence of adverse events of special monitoring (AESM)

2.3 Study design and conduct

This is a Phase 3, multicenter, double-blind, randomized, placebo-controlled study with rozanolixizumab in study participants with persistent or chronic primary ITP defined as more than 3 months, or 12 months of duration, respectively, since diagnosis.

The study participants will be male and female adults with persistent or chronic primary ITP, a platelet count measurement at Screening and at Baseline with an average of the two $<30 \times 10^9/L$ (no single count may be $>35 \times 10^9/L$) and a documented history of low platelet count prior to Screening.

The primary objective of TP0003 is to evaluate the clinical efficacy of rozanolixizumab as a maintenance treatment in participants with persistent or chronic primary ITP.

The study will assess whether multiple sc infusions of rozanolixizumab will result in a durable Clinically Meaningful Platelet count increase of $\geq 50 \times 10^9/L$, for at least 8 out of 12 weeks during the last 12 weeks of the Treatment Period (Week 13 to 25). On Day 1 (Baseline Visit), study participants will be randomized 2:1 to receive a fixed-unit dose of rozanolixizumab [REDACTED] or placebo QW until Week 24, with randomization stratified by the degree of thrombocytopenia (platelet count $<$ or $\geq 15 \times 10^9/L$) and history of splenectomy (yes or no). The last assessments prior to the SFU Visit will be done at Week 25. Study participants will be observed during the 8-week SFU Period after the final administered dose.

Note: As all study participants for the analysis were enrolled under previous protocol versions, they were randomized to receive a fixed-unit starting dose of rozanolixizumab [REDACTED] or placebo. Following the initial dose, study participants were receiving a fixed unit dose [REDACTED] rozanolixizumab or placebo Q2W until Week 23.

The total maximum study duration per study participant is up to 35 weeks, including a Screening Period (up to 4 weeks), a Dose Adaptation Period (12 weeks), a Maintenance Period (12 weeks) and an SFU Period (8 weeks after final dose administered). Splenectomized participants will be required to attend a Prolonged Screening Period prior to the Screening Visit in order to receive, if applicable, the required vaccinations, which will extend the total study duration by up to 20 weeks.

The eligibility of study participants to participate in the study will be determined during the Screening Period. Once eligibility is confirmed, the study participants will come to the site on Day 1 (Baseline Visit) and receive a single fixed-unit dose of rozanolixizumab or placebo administered sc (based on randomization).

Rozanolixizumab or placebo will be administered as a sc infusion with an infusion pump at a [REDACTED]. A fixed-unit dose across different body weight tiers, as presented in Table 1-2 in the study protocol will be applied.

The placebo arm will use 0.9% sodium chloride aqueous solution (physiological saline, preservative-free) for sc administration, matching the volumes of the rozanolixizumab arm. Dosing will be followed by a series of postdose study assessments on Day 1 through Day 169, with a subsequent SFU Period through Day 218. On dosing days, for the first 2 weeks, a 4-hour post-dose observation will be in place. Assuming the first 2 doses were well tolerated, on dosing days in Week 3, 4, and 5, a 1-hour post dose observation will be in place. Assuming the first 5 doses were well tolerated, on subsequent weeks, a 15-minute post-dose observation will be in place. However, if the dose needs to be decreased due to a TEAE(s) or dose needs to be increased, post dose observation will be extended to 1 hour after the end of infusion for the next 2 infusions. The post-dose observation time frame may be extended at the discretion of the investigator. These recommendations are applicable for dosing at site and at home. Approval from the investigator and sponsor is required prior to the start of home dosing.

Note: All study participants for the analysis described in this SAP were enrolled under previous protocol versions and randomized to bi-weekly dosing. SFU Period was until Day 211. For the first three infusions, they were expected to stay at the study site for 4 hours after the end of infusion, and 2 hours after the IMP infusion for the remaining visits until W23. If needed, observation time at site could be extended for each study participant.

In exceptional circumstances (eg, pandemic, hurricanes, etc) where study-specific investigations may not be conducted according to study protocol, contingency measures will be in place (see Section 8 in the study protocol for details).

Approximately 150 study participants were planned to be screened at approximately 70 sites from North America, Europe and Asia to achieve the targeted number of approximately 60 evaluable study participants randomized to weekly dosing.

Note: Due to a strategic decision, the study was stopped early after 33 participants were randomized to bi-weekly dosing per previous protocol versions. Thus, no participants were randomized to weekly dosing in the study per Protocol Amendment 3.

All study participants completing the Treatment Period (with or without the need for rescue therapy) and fulfilling the OLE study (TP0004) eligibility criteria will be allowed to enroll into TP0004.

If study participants require rescue therapy during the Treatment Period (Week 1 to Week 25), they were allowed to receive commercially available rescue therapy (Section 6.4.3 in the study protocol).

An external IDMC was established to review the safety data at predefined intervals and ad hoc as needed, should emerging safety concerns arise during the study. The first IDMC meeting for the review of safety data was planned to occur after approximately 15 participants had received 3

doses of IMP in TP0003 or TP0006. The study was to be put on hold if any of the following occurred:

- The IDMC judges it necessary for medical or safety reasons and
- The sponsor or its designee judges it necessary for medical, safety, regulatory, or any other reasons consistent with applicable laws, regulations and Good Clinical Practice.
- Three study participants experience any SAE of same type within the first 15 study participants who have received 3 doses of IMP across TP0003 and TP0006, unless the SAE is clearly unrelated to the study drug. After Protocol Amendment 3, this rule no longer applied.
 - For US and Canada only: Three study participants experience any SAE within the first 15 study participants who have received at least one dose of IMP across TP0003 and TP0006, unless the SAE is clearly unrelated to the study drug.

The IDMC has the possibility to unblind the data. Details of the IDMC composition, processes, and responsibilities will be documented in the IDMC charter. It is intended to have one IDMC for both of the pivotal studies (TP0003 and TP0006), where the data will be presented unpooled, ie, data from each study will be reviewed separately. Key safety data may be pooled at the discretion of the IDMC for protection of all study participants if warranted.

Based on feedback from the IDMC, weekly dosing was suggested and it was implemented in protocol amendment 3. Study participants being treated with the bi-weekly dosing regimen would switch to the weekly dosing regimen once protocol amendment 3 was approved at the respective study site.

Note: No study participants were actually switched to weekly dosing or started on weekly dosing prior to the termination of the study.

Additionally, a Safety Signal Detection Team performed rozanolixizumab program-wide aggregated safety data reviews at predefined intervals.

2.4 Determination of sample size

Following Protocol Amendment 3, the sample size calculation was amended to reflect the primary objective of assessing the treatment effect on participants who were randomized to weekly infusions. To achieve the study objectives within the sample size cap of the original 2-stage adaptive design, the futility assessment and option for a sample size re-assessment were no longer considered and the sample size calculation was amended as appropriate for a fixed parallel group design.

The observed durable platelet response rates (platelet count $\geq 50 \times 10^9/L$ during 6 or more of the last 8 weeks of treatment), from Kuter et al (2008) in splenectomized participants were 38% (16/42) on active and 0% (0/21) on placebo. In non-splenectomized participants the rates were 61% (25/41) and 5% (1/21), respectively.

Using the true response rate of 0.45 versus 0.05, a sample size of 60 participants randomized in a 2:1 ratio (ie, $n=40$ on rozanolixizumab and $n=20$ on placebo) receiving weekly infusions would provide >90% power to detect a statistically significant difference between treatment groups using Fisher's Exact Test at an alpha level of 0.025 (1-sided).

By definition participants who dropout of the study are determined as nonresponders and are incorporated in the overall response rate. If the number of dropouts is greater than anticipated by 10%, the impact on the rozanolixizumab response rate would mean that it would drop to a response rate of 0.4. In such cases, the study would still achieve >80% power if the overall response rate on placebo remains at 0.05.

If the response rate on placebo was 0.1 rather than the anticipated 0.05, the rozanolixizumab rate would need to be >0.45 to achieve 80% and >0.5 to achieve 90% power. Table 2-1 provides power estimates for a fixed study design of n=60 participants in a 2:1 randomization ratio.

Table 2-1: Expected sample size

Scenario	Placebo Response Rate of 0.05			Placebo Response Rate of 0.1		
	RLZ	Placebo	Power ^a	RLZ	Placebo	Power ^a
1	0.30	0.05	56%	0.30	0.10	32%
2	0.35	0.05	73%	0.35	0.10	48%
3	0.40	0.05	85%	0.40	0.10	63%
4	0.45	0.05	93%	0.45	0.10	77%
5	0.50	0.05	97%	0.50	0.10	87%
6	0.55	0.05	98%	0.55	0.10	93%

^a Power for a Parallel Group Design with N=60 in a 2:1 randomization test computed with Fisher's exact test using NQuery Advisor 7.0.

Note: Due to sponsor decision, the study was stopped early after 33 study participants were randomized to bi-weekly dosing per previous protocol versions. Thus, no study participants were randomized to weekly dosing in the study per Protocol Amendment 3 and all analyses will be conducted on the first 33 study participants who had bi-weekly dosing.

3 DATA ANALYSIS CONSIDERATIONS

3.1 General presentation of summaries and analyses

Statistical analysis and generation of tables, figures, participant data listings, and statistical output will be performed using SAS® Version 9.4 or higher (SAS Institute, Cary, NC, USA).

All tables and listings will use Courier New font size 9.

Descriptive statistics will be displayed to provide an overview of the study results. For continuous variables, descriptive statistics will include number of participants with available measurements (n), mean, standard deviation (SD), the median, minimum, and maximum.

For categorical variables, the number and percentage of participants in each category will be presented. Unless otherwise noted, the denominator for percentages will be based on the number of participants included in the respective analysis set. Participants with missing data can generally be accounted for using the following approaches:

-
- For summaries of demographics and Baseline characteristics: summarize percentages based on all participants in the analysis set and include a “Missing” category (corresponding to participants with missing data for the variable being summarized) as the last row in the list of categories being summarized.
 - For summaries of efficacy and safety variables, unless otherwise specified: summarize percentages based only on those participants with observed data for the variable being summarized. As the denominator may be different from the number of participants in the analysis set being considered, the denominator should be displayed in the table. The general format for displaying this will be “n/Nsub (%)”

Unless otherwise noted, all percentages will be displayed to one decimal place. No percentage will be displayed for zero counts, and no decimal will be presented when the percentage is 100%.

For the purpose of the tabulations the lower and upper confidence limits for the percentages will be truncated at 0 and 100% respectively.

For PK concentrations, summary statistics will include geometric mean, geometric coefficient of variation (CV), 95% confidence intervals (CIs) for geometric mean, arithmetic mean, SD, median, minimum, and maximum. All summaries of PK variables will be based on the observed values. No imputation will be used.

Decimal places for descriptive statistics will always apply the following rules:

- “n” will be an integer
- Mean, SD, and median will use one additional decimal place compared to the original data
- CV [%] will be presented with one decimal place
- Minimum and maximum will have the same number of decimal places as the original value.

If no participants have data at a given time point, for example, then only n=0 will be presented. However, if n<3, present the n, minimum and maximum only. If n=3, n, mean, median, minimum and maximum will be presented only. The other descriptive statistics will be left blank.

Derived variables in general will display the mean, SD and median to 1 more decimal place than the variables used in the derivation. If the number of decimal places reported in the raw data is varied, then use either the maximum raw number of reported decimal places or 3, whichever is the lowest, as a guide for the descriptive statistics.

3.2 General study level definitions

3.2.1 Analysis time points

All data will be analyzed based on the visits identified per the Schedule of Activities in the protocol.

Note: As no study participants were randomized under Protocol Amendment 3 the visit schedule and associated activities relate to those of earlier protocol versions.

Mapping to visit windows will not be applied. For Early Withdrawal visits refer to Section 3.2.3.

3.2.1.1 Relative day

Relative day for an event will be derived with the date of the first sc infusion of study drug as reference.

Relative days for an event of measurement occurring before the date of first sc infusion will be prefixed with '-' and are calculated as follows:

$$\text{Relative Day} = [(\text{Event Date} - \text{Date of First Infusion})]$$

The relative day for an event or measurement occurring on or after the reference date to the date of the last infusion is calculated as follows:

$$\text{Relative Day} = [(\text{Event Date} - \text{Date of First Infusion}) + 1]$$

For events or measurements occurring after the date of the last sc infusion, relative day will be prefixed with '+' in the data listings and will be calculated as follows:

$$\text{Relative Day} = [(\text{Event Date} - \text{Date of Last Infusion})]$$

There is no relative Day 0. Relative day is not calculated for partial dates in cases where relative day is shown in a participant data listing. In such cases, relative day should be presented as '- -' in the participant data listings.

3.2.2 Study periods

The following study periods are defined for this trial:

- Prolonged Screening Period: splenectomized participants will be required to attend a Prolonged Period prior to the Screening Visit for the assessment of vaccination titers and to receive, if applicable, the required vaccinations, which will extend the total study duration by up to 20 weeks.
- Screening Period (up to 4 weeks): Starts at the time of the informed consent date and ends the day before the first dose administration of study drug (i.e. generally the day before Day 1 visit date).

Note: after signing the ICF splenectomized participants will go first through the Prolonged Screening Period and then to the Screening Period, while the non-splenectomized will go directly to the Screening Period.

- Dose Adaptation Period (12 weeks): Starts on the day of the first dose administration of study drug (Day 1) and ends after the Week 13 visit assessments.
- Maintenance Period (12 weeks): Starts on the day after the 12-week Dose Adaptation Period (Week 13) and ends after the Week 25 visit assessments (or at the Early Withdrawal (EW) Visit for study participants withdrawn from the study before Week 25 visit).
- Treatment Period: Starts on the day of the first dose administration of study drug (Day 1) and ends after the Week 25 visit assessments (or at the EW Visit for study participants withdrawn from the study before Week 25 visit). It is the combination of the Dose Adaptation Period and the Maintenance Period.
- Safety Follow-up Period (SFU): Starts with last dose administered and ends 8 weeks after final dose administered.

A study participant is considered to have completed the study if he/she has completed all phases of the study including the SFU Period or has successfully been enrolled (completed Visit 1 in TP0004) into TP0004 at Week 25.

A study participant will be said to have completed the SFU period if she/he had completed the last scheduled visit in the SFU period.

Study participants will have an EOS Visit performed 8 weeks after the final dose of IMP (unless they are enrolling in TP0004 at Week 25), or upon discontinuation of the study.

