All study participants completing the Treatment Period (regardless of whether they received rescue therapy or not) and fulfilling the open-label extension (OLE) study (TP0004) eligibility criteria will be allowed to enroll into the 1-year OLE treatment study TP0004. The enrollment into the TP0004 study should be conducted on the same day as Visit 27 (Week 25) of the feeder study. In case the enrollment into TP0004 is not conducted at Week 25 (Visit 27), a visit window of +3 days will be granted; therefore, rollover needs to be completed 3 days after Week 25 at the latest.

Participants that will not be enrolling into the OLE study will be followed for up to 8 weeks after the last administration of IMP. The End of Study (EOS) Visit will be performed after the SFU Period.

An external Independent Data Monitoring Committee (IDMC) will be established to review the safety data at predefined intervals and ad hoc as needed should emerging safety concerns arise during the study. The first IDMC meeting for the review of safety data is planned to occur after approximately 15 participants have received 3 doses of IMP in TP0003. The study will be put on hold if any of the following occurs

- The IDMC judges it necessary for medical or safety reasons and
- The sponsor or its designee judges it necessary for medical, safety, regulatory, or any other reasons consistent with applicable laws, regulations and Good Clinical Practice.
- Three study participants experience any serious adverse event (SAE) of the same type within the first 15 study participants who have received 3 doses of IMP across TP0003 and TP0006, unless the SAE is clearly unrelated to the study drug.
 - **For US and Canada only:** Three study participants experience any SAE within the first 15 study participants who have received at least one dose of IMP across TP0003 and TP0006, unless the SAE is clearly unrelated to the study drug.

It is intended to have one IDMC for both of the pivotal studies (TP0003 and TP0006), where the safety data will be initially presented unpooled, ie, data from each study will be reviewed separately. Key safety data may be pooled at the discretion of the IDMC for protection of all study participants if warranted.

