5 STUDY POPULATION CHARACTERISTICS

5.1 Subject disposition

The following outputs will be created.

Summaries:

- **Reasons for screen failures** (as collected on the Study Termination Screen Failure CRF page) will be summarized using the ES for overall for all screened study participants who failed to be randomized.

-
- **Disposition of study participants screened** will be summarized using the ES for overall, by region and by site. In this summary, the site number, principal investigator name, first subject in date, last subject out date, will be captured by randomized treatment, and by each analysis set (ES, RS, SS, PK-PPS).
 - **Disposition of Analysis Sets:** summary of disposition of study participants by treatments group, by analysis sets (ES, RS, SS, and PK-PPS) using the RS.
 - **Disposition and Discontinuation Reasons**, using the RS, will contain the number and percentage of study participants who:
 - Started study and started each study period (Dose Adaptation Period, Maintenance Period and SFU Period)
 - Completed the study and completed each study period study period (Dose Adaptation Period, Maintenance Period and SFU Period)
 - Discontinued study and discontinued in each study period (Dose Adaptation Period, Maintenance Period and SFU Period)
 - Primary Reason for discontinuation (premature study termination as collected in the Study Termination CRF)
 - **Discontinuation due to AEs**, using the RS to tabulate the total number of study participants who discontinued the study due to AEs by treatment group, and the categories: AE serious, fatal, AE non-fatal and other (AE non-serious, fatal).
 - **COVID-19 Disposition:** Disposition and discontinuation reasons using the RS will contain the number and percentage of study participants who started, completed and permanently discontinued Treatment Period / Observation Period overall and by pre-, and during the COVID-19 pandemic based on the start, completed and discontinuation date relative to the pandemic cut-off date. The pandemic start date is March 20, 2020. The discontinuation reason in each period will also be summarized. Discontinuation due to COVID-19 pandemic will be listed as sub-category under “Other” reason.

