6.5.1 Assignment of medications to treatment period

- **Treatment Period:** The treatment period will include medications taken at least once between the first administration of IMP on Day 1, up to the earliest of:
 - Week 25 (for participants who roll over to TP0004)
 - [REDACTED] after the last dose of IMP
 - The early withdrawal visit.
- **Safety Follow-Up Period:** A medication will be assigned to the Safety Follow Up Period if it has been taken at least once from the day after the end of the Treatment Period up until the EOS visit.

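### SAP 3.2.2 starts Safety Follow-up at the last dose, inside the Treatment Period, so the SFU rows of the disposition table show dosed TP0004 rollovers as starting follow-up but never completing it

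*SAP*

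**What the plan says.** SAP 3.2.2 (Study periods) gives the follow-up definition as "Safety Follow-up Period (SFU): Starts with last dose administered and ends 8 weeks after final dose administered". In the same list it defines "Treatment Period: Starts on the day of the first dose administration of study drug (Day 1) and ends after the Week 25 visit assessments". Early withdrawals instead leave that period when they attend their EW Visit. The Maintenance Period has the same end.

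Completion is defined separately, and by visit: "A study participant will be said to have completed the SFU period if she/he had completed the last scheduled visit in the SFU period". At study level, a participant also counts as a completer who "has successfully been enrolled (completed Visit 1 in TP0004) into TP0004 at Week 25".

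SAP 5.1 (Subject disposition) then tabulates participants who "Started study and started each study period (Dose Adaptation Period, Maintenance Period and SFU Period"), with matching rows for completed and discontinued. It writes no exception for rollovers and no rule for choosing the period to which a discontinuation belongs.

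Other parts of the documents place follow-up later. SAP 6.5.1 assigns medications to follow-up if taken "from the day after the end of the Treatment Period up until the EOS visit". SAP 10.2.1 assigns adverse events to follow-up once more than 7 days have passed since the final dose. Protocol 7.1.3 and 7.2 have withdrawn participants attend the EW Visit and then enter SFU. The Protocol synopsis limits follow-up to those not rolling over: "Participants that will not be enrolling into the OLE study will be followed for up to 8 weeks after the last administration of IMP".

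**The concern.** A by-period disposition table works only if the periods follow one another and each participant's entry and exit are defined consistently. Here the start of SFU is triggered by a dose, its completion by a visit, and the end of the preceding period by a different visit. Rollovers pass the start trigger but are never scheduled for the completion visit. They would appear as follow-up losses even though follow-up in this study was not intended for them. In a study stopped early and reported descriptively, disposition is one of the main tables a reader relies on, and a gap between SFU started and SFU completed would be read as attrition.

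**Working it through.** **Inputs.** Bi-weekly dosing until Week 23 for all analysed participants (SAP 2.3, note). SFU for them until Day 211 (SAP 2.3, note). Under Amendment 3: weekly dosing until Week 24, assessments to Day 169, SFU to Day 218, maximum duration 35 weeks (SAP 2.3). Number randomized: 33 (SAP 2.3 and 2.4). Visit day = 7 × (Week − 1) + 1.

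**Reproducing the plan's own figures.**
- Weekly: last dose 7 × 23 + 1 = Day 162; 162 + 56 = Day 218, as stated. Duration 4 + (218 − 1)/7 = 4 + 31 = 35 weeks, as stated.
- Bi-weekly: last dose 7 × 22 + 1 = Day 155; 155 + 56 = Day 211, as stated.
- The periods listed for the weekly design sum to 4 + 12 + 12 + 8 = 36 weeks. The stated 35 therefore already implies one week shared between Maintenance and SFU.

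**Overlap under SAP 3.2.2.** Week 25 = 7 × 24 + 1 = Day 169.
- Bi-weekly completers: 169 − 155 = 14 days (Day 155 to Day 169).
- Weekly schedule, not used by any participant: 169 − 162 = 7 days.
- Early withdrawals: from the last dose to the EW Visit, whatever that interval is.

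**Rollovers in the SFU rows.** Every dosed participant has a last dose, so every dosed participant meets the SFU start definition. Completion needs the last scheduled SFU visit. SAP 10.1, in its time-at-risk rule, states that participants continuing into the open-label study have no SFU visit in the parent study. So each dosed rollover is a starter who cannot complete. The number affected equals the number of dosed rollovers. The documents do not give it, so the range is 0 to at most 33.

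**Withdrawals.** There are three cases under the literal definitions.
- The participant attends the EW Visit and later the EOS Visit: SFU is completed, and the discontinuation belongs to a treatment period only.
- The participant leaves between the last dose and the EW Visit and does not finish SFU: the date lies in a treatment period and in SFU, and SAP 5.1 does not say which one to count. Counting both is possible.
- The participant completes Week 25, does not roll over, and is lost afterwards: SFU only.

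No count can be computed for the second case, because the documents give no withdrawal numbers.

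**After the correction.** Overlap is 0. SFU lasts (211 − 169)/7 = 6 weeks for the bi-weekly schedule and (218 − 169)/7 = 7 weeks for the weekly one. The end dates, Day 211 and Day 218, do not move.

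**Knock-on check with SAP 10.2.1.** The adverse event cut is last dose + 7. On the weekly schedule this is 162 + 7 = Day 169, the same as Week 25. On the bi-weekly schedule it is 155 + 7 = Day 162, so events starting on Days 163 to 169 go to SFU while SAP 3.2.2 still places those days in the Treatment Period.

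**The case against.** The strongest reply is that this is loose wording with little consequence. The Protocol itself describes SFU as 8 weeks from the final dose, and the SAP repeats that. SAP 3.2.2 counts TP0004 enrolment as study completion and exempts rollovers from the EOS Visit, so they cannot be reported as study discontinuations. Adverse events and medications have their own non-overlapping assignment rules (part of the medication rule is redacted, so its full relation to 3.2.2 cannot be checked). A sensible programmer could assign one period per participant from the single Study Termination form. Most of this stands, and it sets the limits of the point. It does not remove the rollover problem: the started and completed rows for SFU follow from written definitions, and no exception is written.

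A reader might infer three stronger claims, and the documents support none of them.
- *All on-treatment withdrawals are double-counted.* Overlapping dates are not the same as two counted discontinuations. SAP 5.1 does not call for counting in every period that contains the date, it takes one primary reason per participant, and a withdrawn participant who attends EOS has completed SFU.
- *The overlap hides where participants left relative to the Week 14 to 25 endpoint window.* That information sits in the Dose Adaptation and Maintenance rows, which the SFU definition does not change. Missing platelet counts are set to zero regardless of period (SAP 4.2.1).
- *Week 25 laboratory and vital-sign values are tabulated twice.* SAP 10 does mention presentation by period, but the marked-abnormality summaries are specified by timepoint (SAP 10.3.1 and 10.5), and data are analysed by scheduled visit without window mapping (SAP 3.2.1).

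**Conclusion.** The point holds within narrow bounds. SAP 3.2.2 makes SFU overlap the Treatment Period by 14 days for bi-weekly completers, and from last dose to EW Visit for early withdrawals. This conflicts with the order of events in the Protocol. Applied as written in SAP 5.1, it reports every dosed TP0004 rollover as having started and not completed SFU, and it leaves open a double count for participants who leave between the last dose and the EW Visit without finishing SFU. The size is between 0 and all of the up to 33 participants for the first effect and unknown for the second. The conclusion assumes that the table is programmed from the literal definitions. It concerns only the SFU rows of one descriptive table; efficacy summaries, overall study completion, and the adverse event and medication tables do not change.

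**What to change.** Replace the SFU definition in SAP 3.2.2 along these lines: *For participants who do not enrol in TP0004, SFU starts the day after the Week 25 or EW Visit and ends at the EOS Visit, 8 weeks after the final dose. Participants who enrol in TP0004 have no SFU Period.* Then add four short statements:

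1. A fallback start date for participants with neither a Week 25 nor an EW Visit, for instance those lost to follow-up. The 7 days after final dose already used in SAP 10.2.1 would serve.
2. The denominator for the SFU rows in SAP 5.1 is the number of participants who entered SFU.
3. Each discontinuation is assigned to one period only, by a stated rule.
4. The 7-day adverse event cut in SAP 10.2.1 is either aligned with this definition or declared a separate rule, given that it differs from Week 25 by 7 days on the bi-weekly schedule.

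The cost is a few lines of SAP text and minor programming. No new data are needed, and the follow-up end dates stay as they are.
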